## **4a. Location.**

All study activities will occur at the University of Texas at Austin. The cardiovascular assessments will occur in the Cardiovascular Aging Laboratory of [name], a research-dedicated facility in Bellmont Hall. Cognitive testing will occur in the Clinical Neuroscience Laboratory of [name], Seay building. The fMRI testing will occur in the Imaging Research Center (IRC) located in the Norman Hackerman Building. The laser treatment will be done in the dedicated room in the [name] laboratory in Seay 3.304. This room has already been evaluated and posted by the UT Austin Laser Safety Program for the use of the HD laser apparatus.

## **4b. Resources.**

This research will be supported by NIH grant R21AG050898 and a grant by the Darrell K Royal research fund for Alzheimer's disease.

## **4c. Study Timeline.**

We anticipate that this study will take three years to gather data and one year to analyze and disseminate the results.

## **5. Measures:**

The PVT and DMS are implemented by a program called PEBL, the Psychology Experiment Building Language, an open-source programming language. For the PVT, this file includes dependent variables for each trial, such as reaction time in milliseconds, as well as a code number indicating whether the trial was a success (response in less than 30 seconds), a lapse (no response in 30 seconds), or a false alarm (responded with a button press prior to the onset of the cue). Participants will be identified by a code number (their randomly-assigned subject number) typed into the program, prior to the start of each block of trials. For the DMS, the dependent variables include reaction time in milliseconds, and success/failure on the choice part of the task; participants are indexed by their randomly-assigned number. For the intima media thickness (IMT) measurements, ten measurements will be averaged to give a final value; this data will also be encoded using the participant's randomly-assigned subject number. The fMRI data consist of a Blood Oxygen Level Dependent (BOLD) contrast imaging signal which

# Research Proposal

---

shows brain metabolic activity; these measures will also be recorded under each participant's randomly-assigned subject number. Additional measures used for sample characterization (also indexed with each participant's randomly-assigned code number) include responses to the questionnaires seen in the uploaded attachment Cognitive Test Packet.pdf (which includes Medical Screening Questionnaire, Food Diary, Edinburgh Handedness Questionnaire, Beck Depression Inventory, State Trait Anxiety Questionnaire, Cognitive Difficulties Scale, and 36-Item Short Form Survey Instrument (SF-36)).

## **6. Participants:**

### **6a. Target population and subject numbers.**

Men (n=100) and post-menopausal women (n=100), aged >45, of any ethnic background from the surrounding community will be considered for the study. Equal numbers of men and women are expected to enroll. Racial and ethnic composition is expected to reflect that of the state of Texas. Participants will not be excluded on the basis of gender, race, ethnicity, or socioeconomic status.

### **6b. Inclusion/exclusion.**

The primary inclusion criterion is age: subjects must be 45 years old or older. However, there are a number of exclusionary criteria. (Please see attachment: Exclusionary criteria screening checklist.docx.) Female participants will be limited to post-menopausal women. The criteria will be such that participants will be excluded that have been diagnosed with a psychotic disorder, have a history of violent behavior, are currently pregnant, or have ever been institutionalized or imprisoned. Participants with subjective complaints regarding modest decline cognitive decline from a previous level of performance will be included as long as the cognitive deficits do not interfere with their capacity for independence in everyday activities (Clinical Dementia Rating Score=0 or 0.5). Participants with CDR=0.5, who were randomly assigned to the placebo-treated group, will be given the chance to return for 6 weeks of active therapy. Thus, they will have the option to receive the potential benefits from LLLT. These visits will be offered as a courtesy and participants will not receive additional monetary compensation for them.

For the MRI, participants will be excluded if they have a history of neurological disease (e.g., large vessel stroke, seizure disorder, Parkinson's disease, clinically significant traumatic brain injury, multiple sclerosis, or brain infection/meningitis), major psychiatric illness (e.g. schizophrenia, bipolar disorder), MRI contraindications, including BMI > 40, or show evidence of large vessel stroke or clinically significant white matter disease confirmed by a licensed neuroradiologist. Participants with MCI with MRI contraindications will be enrolled in the study, but will not complete MRI scanning. Excluded participants will be encouraged to see their primary care physician for further care. Uninsured participants will be provided with low cost medical care resources in the Austin area organizations.

### **6c. Benefits.**

There is no guarantee of direct benefits; however, our previous work (Barrett and [name] 2013, Hwang, Castelli and [name] 2016) successfully demonstrated the beneficial effects of LLLT on sustained attention and working memory tasks, as well as

executive function (Blanco, Maddox and [name] 2015) and alleviating symptoms of depression (Disner, Beevers and [name] 2016), providing evidence for LLLT as a non-invasive, easily administered, and clinically useful tool to augment brain activity. These results suggest that LLLT could be a way to increase a subject's ability to sustain attention for longer periods of time, and even provide a non-invasive, non-pharmacological treatment for disorders such as attention deficit disorder, which may be useful for subjects that are treatment-unresponsive to drugs like Ritalin, or who simply do not want to be treated pharmacologically for such a disorder. Similarly, the beneficial effect on mood indicates that LLLT could provide a non-invasive, non-pharmacological, easily administered and clinically useful way to treat mood disorders. Participants can also elect to receive feedback from their cognitive and cardiovascular testing (see attachments: Cognitive feedback letter template.doc; Cardio feedback letter template.doc).

### **6d. Risks.**

As an NIH-NIA funded study, this study is registered as a clinical trial (NCT02851173) and subject to oversight by an NIA-approved external Data Safety and Monitoring Board. The three members of the DSMB are: [name]. UGA (Chair); [name]., Brown (Safety Officer), and L. [name]. UGA (member). A copy of the Data and Safety Monitoring Plan will be uploaded separately (see attachment: DSMP.doc). In this DSMP is a complete description of the Risks (section 1.1), Adverse Event and Serious Adverse Event Collection and Reporting (section 1.2), and Protection against Study Risks (section 1.3).

**Possible Discovery of Findings Related to MRI.** The MRI scans (which possibly could result in claustrophobia as a possible risk) that will be performed are NOT necessarily equivalent to those used to diagnose medical problems. Many potentially serious problems may be undetectable on these scans and ultrasounds. A lack of findings should not be used to avoid physician visits. Participants who have are having physical symptoms that they find concerning will be encouraged to see their primary physician, who will determine the examinations required to arrive at a proper medical diagnosis.

The MRI scans will produce anatomical images that may be reviewed by a certified radiologist. In the unlikely event that the images show clinically significant findings, the investigator will contact the participant and inform him or her of the findings. The initial contact will be by phone and followed up with a letter. Two weeks after the initial contact, the participant will be called again to see if he or she needs any further assistance. The participant will be told that the decision as to whether to proceed with further examination or treatment lies solely with the participant and his or her physician. The participant will be informed that the investigators, the consulting radiologist, and The University of Texas are not responsible for any medical examination or treatment that the participant may undertake based upon our findings. Because the images obtained in this study do not comprise a proper clinical MRI study, these images will not be made available to the participant or his or her physician.

The Imaging Research Center has an approved protocol in place regarding the possible discovery of findings, and that protocol will be followed. The specific steps to be carried out to inform the participant of potentially problematic findings are as follows:

1-Images with suspected incidental findings will be flagged and reported to the IRC. They will be referred to [name], a licensed neuroradiologist and medical director of the IRC, for interpretation.

2-Should contact with the participant is deemed appropriate by [name], the participant will be contacted and a phone conference arranged during which [name] can explain the incidental findings to them and offer advice about follow-up care.

3-The phone call will be followed up with a letter summarizing the findings and recommendations.

### 6e. Recruitment.

Participants will be recruited using newspaper/craigslist advertisements, and flyers posted around the greater Austin area and at various organizations (please see attachments: Newspaper advertisement text.doc; Flyer.ppt) To facilitate recruitment of participants with mild cognitive impairment, we have added recruitment materials that specifically target this population (see uploaded documents: Newspaper advertisement text MCI.docx; Flyer\_MCI.ppt). Participants will contact the lab and complete a brief screening form over the phone or online via Research Electronic Data Capture (REDCap) to determine if they meet the inclusion criteria and would like to participate (please see attachments: Recruitment telephone script.docx; Exclusionary criteria screening checklist.docx; see below for information on REDCap).

Additionally, participants from previous IRB-approved studies conducted by our lab, whose consent forms did not preclude future contact, will be contacted about enrollment in the current study. Participants who do not wish any future contact will be placed on a no-contact list. If participants have not responded to the invitation to contact the lab after three messages, they will be moved to the no-contact list. Participants from previous studies who are interested in participating in the current study will complete a brief screening form over the phone or online to ensure continued eligibility (please see attachments: Recruitment telephone script.docx; Exclusionary criteria screening checklist.docx).

Screening forms collected online, and contact information for participants who have agreed to be recontacted for future studies, will be managed using REDCap. REDCap is a secure web application designed to support data capture for research studies, providing user-friendly web-based case report forms, real-time data entry validation (e.g. for data types and range checks), audit trails and a de-identified data export mechanism to common statistical packages (SPSS, SAS, Stata, R/S-Plus). REDCap also provides a powerful tool for building and managing online surveys. The research team can create and design surveys in a web browser and engage potential respondents using a variety of notification methods. The system was developed by a multi-institutional consortium which includes University of Texas at Austin and was initiated at Vanderbilt University. Network transmissions (data entry, survey submission, web browsing, etc.) in REDCap are protected via Secure Sockets Layer (SSL) encryption. REDCap data collection projects rely on a thorough study-specific data dictionary defined in an iterative self-documenting process by all members of the research team with planning assistance from the PRC. The iterative development and testing process results in a well-planned data collection strategy for individual studies. REDCap provides a secure, web-based application that is flexible enough to be used for a variety of types of research, provide an intuitive interface for users to enter data and have real time validation rules at the time of entry.

## **6f. Obtaining Informed Consent.**

While the consent form will be mailed as part of the Mailing Packet to interested participants, informed consent will be obtained while the PI or research assistants are present, when the participants come to their first appointed experiment time. One of the researchers will guide the participants through the consent form with an oral explanation, and then the participant will be given the opportunity to read through the consent form. When this is completed, the researcher will ask if there are any questions or concerns. The consent form will be signed and confidentially kept in a locked file cabinet. Participants chosen to be scanned with MRI will fill out a separate consent form.

Participants will be asked to provide consent to be contacted in the future regarding opportunities to participate in any follow-up components to the present study, pending continued grant funding. Participants who do not wish future contact are able to check an “opt-out” box that will preclude them from future contact.

## **7. Privacy and Confidentiality:**

The data will not be shared by other researchers for research purposes not detailed in this study. Information collected during the initial experiment screening will contain no identifying information until the participant signs the informed consent. No record will be kept of screens of persons determined not eligible for the study, or who decide not to participate. The participant will maintain control throughout the study over the content and amount of information he/she chooses to share with the experimenter, and has the right to withdraw from the study at any time without any penalty. Individuals will participate in the experiment one at a time, to prevent anyone’s choice to participate from becoming public. The performances on the reaction time tasks or the results of the questionnaires of any participant will never be revealed to another participant. Participants can skip any question on any of the questionnaires. The consent and debriefing sessions will also be conducted by a trained investigator. Privacy and confidentiality of participants will always be maintained.

Efforts will be made to ensure participant privacy within the constraints of the study design. The study visits will be scheduled in accordance to the participant’s availability as long as resources are available. These visits will be conducted only in the presence of trained research assistants. Participants will also be contacted by phone or email, depending upon their preference, to schedule appointments and for appointment reminders. Permission to leave messages will be asked at the time of screening.

One important limit or exception to maintaining confidentiality comes in regards to the investigators identifying persons who pose a risk of harm to themselves or others. Under circumstances where any participant is identified as being at imminent risk of harming themselves, confidentiality will be breached to ensure the participant’s safety. In such cases, a report of the risk will be made to the Psychiatric Crisis Services Department of the Austin Travis County Integral Care Center. If a subject indicates current suicidal ideation, we will contact the Behavioral Concerns Advice Line.

Regarding confidentiality of the research data, documents with participants’ identifying information will be placed in a locked file cabinet located at the Department of Psychology. All data is represented using the participant’s randomly-assigned subject number, not their name. Network transmissions (data entry, survey submission, web browsing, etc.) in REDCap are

## Research Proposal

---

protected via Secure Sockets Layer (SSL) encryption. Images collected during the MRI scan and ultrasound sessions will be stored on a Department of Psychology server under study and scan number. Personal information linking a participant with data will be maintained in a separate secure document, which is destroyed at the end of the experiment. Department of Psychology servers are backed up on a daily basis. Access to the scans and databases will be password protected and only available to relevant researchers designated by the PI. The consent forms will be kept for five years and then destroyed. All hard copies will be shredded, and digital copies will be deleted.

Saliva samples awaiting genetic analyses will be stored under participants' study number according to proper storage temperatures in a biosafety level 2 area (SEA 4.111B) until they are transferred to the UT Austin DNA Sequencing Facility (DSF) for analysis.

Anonymized data may be shared with other researchers, upon request, as per NIH guidelines.

### 8. Compensation:

Participants will receive \$200 upon study completion. Should participants wish to discontinue the study early, they will be compensated \$17 per study visit for each completed visit. Subjects will be paid at the end of their last visit, with a check, and they must sign the receipt.

**Statistical Plan:**

1. Primary outcome measure (PVT) will be analyzed using mixed ANOVA with 1 between-subjects factor (Treatment Group) and 1 within subjects factor (Time). Cognitively unimpaired (CU) and MCI groups will be analyzed separately. The contrast of interest will be Treatment Group by Time interaction. Alpha level of significance will be set at 0.05.
  - a. Secondary outcome measures (2Back performance, % Correct and Reaction Time) will be analyzed using mixed ANOVA with 1 between-subjects factor (Treatment Group) and 1 within subjects factor (Time). Cognitively unimpaired (CU) and MCI groups will be analyzed separately. The contrast of interest will be Treatment Group by Time interaction. Alpha level of significance will be set at 0.05.
  - b. Secondary outcome measures (2Back activation intensity within 8 *a priori* ROIs) will be analyzed using mixed ANOVA with 1 between-subjects factor (Treatment Group) and 1 within subjects factor (Time), only for participants who can perform the task to criterion (%Correct>50%). Cognitively unimpaired (CU) and MCI groups will be analyzed separately. The contrast of interest will be Treatment Group by Time interaction. Alpha level of significance will be set at 0.05 due to the exploratory nature of the analysis.
  - c. *A priori* ROIs were chosen based on prior literature. They are as follows:

ROI#	x	y	z	size (mm2)	designation
1	-33	4	56	2087	Left middle frontal gyrus
2	-5	19	44	1651	Left medial frontal/superior frontal gyrus
3	37	-63	53	683	Right superior parietal lobule
4	-49	-52	44	1333	Left inferior parietal lobule
5	-44	45	13	1139	Left middle frontal gyrus
6	33	48	15	955	Right superior frontal gyrus
7	32	5	55	553	Right middle frontal gyrus
8	47	14	3	335	Right inferior frontal gyrus

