## Research Proposal

---

LLLT or placebo will be administered once a week for 6 weeks, following the same stimulation procedure as in our previously-approved IRB protocols (2011-05-0022, 2015-09-0018) and as reported in Barrett and [name] (2013). Administration of LLLT consists of applying light of a specific wavelength (1064 nanometers) using a laser diode, the HD laser (Cell Gen Therapeutics, LLC). This apparatus is FDA-cleared for temporary relief of muscle and joint pain, muscle spasm, stiffness associated with arthritis, improving circulation, and relaxation of muscle tissue. The HD laser has been evaluated and the standard operating procedure reviewed by the University of Texas at Austin Laser Safety Program for the purpose of occupational safety. The individuals who will operate the HD laser have completed the OH 304 Laser Safety class through UT's Environmental Health and Safety office. Both participants and experimenters wear protective eyewear, though the administrators of the LLLT are careful not to shine the light in or near the eyes.

The diameter of the circular surface receiving the LLLT is 4 centimeters. The laser power output used is 3.4 Watts. The irradiance (or power density) used, 250 milliwatts/centimeter, as well as the cumulative fluence (or energy density) used, 60 Joules / centimeter, are the same parameters that showed psychologically beneficial effects in Schiffer et al. (2009) and in Barrett and [name] (2013), and the same parameters approved in our previous approved IRB protocol (2011-05-0022). From ANSI Z136.1-2007, Table 7, the Maximum Permissible Exposure (MPE) to skin at the emission wavelength is 1.0 W/ cm^2. (The MPE standard for this wavelength is unchanged in Table 7b of the 2014 revision of the ANSI Z136.1 Safe Use of Lasers.) At the power level described, the energy emitted by the HD laser at this setting is one quarter of the skin MPE (0.250 W/cm^2), exposure to it is not deemed harmful to tissue, and it causes no detectable physical damage and negligible heat. In fact, similar settings are used clinically by Cell Gen Therapeutics for the treatment of disorders such as lower back pain, sciatica, and migraine headaches.

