# Research Proposal

---

During the treatment visits, LLLT-related cognitive enhancement will be assessed using two tasks: the psychomotor vigilance task (PVT), a test of sustained attention; and the delayed match-to-sample memory task (DMS), a test of visual working memory. These executive/cognitive processes are mediated by the frontal cortical regions that the LLLT treatments target. These tasks are the same as those approved in our previously-approved IRB protocols (2011-05-0022, 2015-09-0018).

The first test will be a pre-treatment baseline evaluation. (This will be preceded by a brief 1-minute-long introduction to both tasks; this data will not be recorded.) Then, after the first treatment with LLLT or placebo, participants will repeat the PVT and DMS tasks. Participants will again repeat the PVT and DMS tasks after the sixth (final) treatment is completed. We have previously demonstrated an improvement in performance on both the PVT and DMS tasks after LLLT treatment (Barrett and [name], 2013).

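### The primary PVT test is a Group-by-Time interaction with no baseline covariate and undefined levels of Time; it is valid, but baseline-adjusted contrasts at named post-tests would be more precise and would say when and in which direction the arms differ.

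*SAP*

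**What the plan says.** SAP, Statistical Plan, item 1: "Primary outcome measure (PVT) will be analyzed using mixed ANOVA with 1 between-subjects factor (Treatment Group) and 1 within subjects factor (Time". It continues: "The contrast of interest will be Treatment Group by Time interaction". Alpha is 0.05, and the CU and MCI groups are analysed separately. The item gives no covariate, no levels of Time, no primary post-test and no follow-up contrast.

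The protocol's account of the treatment visits (section 3, Procedures) sets out three PVT tests:

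- before treatment: "The first test will be a pre-treatment baseline evaluation";
- after session 1: "Then, after the first treatment with LLLT or placebo, participants will repeat the PVT and DMS tasks";
- after session 6: "Participants will again repeat the PVT and DMS tasks after the sixth (final) treatment is completed".

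Neither document ranks the two post-tests. The treatment is a course: "LLLT or placebo will be administered once a week for 6 weeks". Section 2 (Purpose) states a directional hypothesis of better performance, judged against each participant's own baseline.

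**The concern.** Item 1 can be followed in more than one way, and each way leaves something to improve.

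**Two levels of Time** (baseline and one post-test). The interaction is the difference between arms in mean change. It has 1 df, a readable direction, and it fits the Purpose section. But it treats the baseline PVT as an outcome when it could serve as a covariate. That gives up precision that the trial has already paid for, and the loss matters more because the sample is split into CU and MCI.

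**Three levels of Time.** The interaction is a 2-df F test. It does not test at which post-test the arms differ or which arm does better. An effect present only after the first session can make the primary result positive when nothing remains after the six-session course.

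Because Time is undefined, two analysts could follow item 1 faithfully and run different primary tests.

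**Working it through.** **Inputs from the documents:** the model, the interaction test, alpha 0.05, separate CU and MCI analyses, and three PVT tests. The plan states no power figure, so there is none to reproduce.

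**Assumptions, not in the documents:** SD 1 at every test, effect 0.5 SD, two-sided alpha, 1:1 arms, 50 or 25 per arm within a stratum, correlation 0.8-0.9 between same-day tests (baseline and session 1) and 0.5-0.7 between tests five weeks apart.

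**Step 1: two-level Time, precision.** With n per arm, the change-score contrast has variance (2/n) x 2(1-rho). The ANCOVA contrast has variance (2/n) x (1-rho^2). The ratio is (1-rho^2) / [2(1-rho)] = (1+rho)/2. The extra participants needed to match ANCOVA are 2/(1+rho) - 1.

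| Time levels | rho | Variance ratio | Extra participants |
|---|---|---|---|
| Baseline, session 6 | 0.5 | 0.75 | 33% |
| Baseline, session 6 | 0.7 | 0.85 | 18% |
| Baseline, session 1 | 0.8 | 0.90 | 11% |
| Baseline, session 1 | 0.9 | 0.95 | 5% |

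Estimating the slope multiplies the ratio by about 1 + 1/(N-4), where N is the stratum total. At N=20 and rho 0.9 this gives 0.95 x 1.0625 = 1.009, so the gain is gone. At N=50 and rho 0.5 it gives 0.75 x 1.0217 = 0.766, so most of the gain remains.

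**Step 2: two-level Time, power** (noncentral t; df 2n-2 for change, 2n-3 for ANCOVA).

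| n per arm | rho | Change score | ANCOVA |
|---|---|---|---|
| 50 | 0.5 | 0.697 | 0.815 |
| 25 | 0.5 | 0.410 | 0.516 |
| 50 | 0.7 | 0.892 | 0.934 |
| 50 | 0.8 | 0.975 | 0.985 |

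**Step 3: three-level Time, power.** Simulation with 20,000 runs per case over a grid of nine correlation pairs; entries are the minimum and maximum, in percent. GG F is the three-level interaction with the Greenhouse-Geisser correction. Session-6 ANCOVA is one baseline-adjusted contrast. Holm counts at least one rejection among the two baseline-adjusted contrasts.

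| Effect present | n per arm | GG F | Session-6 ANCOVA | Holm, both |
|---|---|---|---|---|
| Session 1 only | 50 | 85-99 | 5 | 97-100 |
| Fading, 0.5 to 0.25 SD | 50 | 74-97 | 29-41 | 97-100 |
| Session 6 only | 50 | 71-92 | 81-93 | 73-89 |
| Both post-tests | 50 | 84-99 | 81-93 | 98-100 |
| Session 1 only | 25 | 45-74 | 5 | 73-96 |
| Fading, 0.5 to 0.25 SD | 25 | 33-63 | 17-23 | 74-96 |
| Session 6 only | 25 | 42-64 | 51-67 | 40-57 |
| Both post-tests | 25 | 45-75 | 51-67 | 81-97 |

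Under the null all three stay at about 5%. The F without a sphericity correction runs at about 5-7%, a minor excess. A smaller rerun at two extreme corners of the grid agreed within simulation error.

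**The case against.** The strongest reply is that the planned test is sound and in common use. With two levels of Time it is unbiased under randomisation and reads directly as a difference in change, as the Purpose section frames it. Baseline adjustment is then a matter of efficiency, and a modest one if Time means baseline and session 1. All of this stands.

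With three levels, the corrected F has more power at 50 per arm than a single session-6 contrast in three of the four profiles. It gives way only when the effect appears after session 6 alone. This also stands: greater precision at one post-test is not greater power against every pattern of effect.

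Holm has its own limits. It can be positive on a session-1-only effect, just as the F can. At 25 per arm it is slightly weaker than the corrected F for a session-6-only effect. What it adds is a label: it says which post-test differs and in which direction.

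A reader might infer that the planned test is invalid, or that a rejection driven by session 1 is a false positive. Neither follows. Such a rejection reflects a real difference between arms, although it does not show benefit after the course. A reader might also infer that the plan intends to pick a follow-up contrast after seeing the data. The SAP plans no follow-up contrast at all. Direction could be read from the arm means at each test; what is missing is a pre-specified test of it.

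**Conclusion.** The point holds as an improvement to a valid primary analysis and should be fixed. The documents establish two facts: item 1 has no baseline covariate, and it leaves Time undefined although three PVT tests are scheduled. No other section settles which reading applies.

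The sizes are illustrative, because rho, the effect, the allocation ratio and the stratum sizes are all assumed. The 18-33% figure belongs only to baseline versus session 6; for baseline versus session 1 it is 5-11%. In a very small stratum with high correlation there may be no gain. Under three-level Time the gain lies in interpretation, with a power trade-off that depends on the pattern of the effect.

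**What to change.** In item 1, for CU and MCI separately, replace the interaction with LLLT-minus-placebo contrasts adjusted for pre-treatment PVT. Use ANCOVA, or a mixed model for repeated measures with unstructured covariance. State which post-test is primary. The sponsor chooses between:

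- (a) one pre-specified post-test as primary, with the other secondary;
- (b) both post-tests, with Holm at 0.05.

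Adjust 2-Back performance for its baseline value in the same way. For the ROI analysis, which the SAP calls exploratory, this is optional.

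**Cost.** Only SAP wording changes; every PVT test is already scheduled. If (a) names session 6, power against a fading effect is much lower than with the corrected three-level F, and a session-1-only effect is detected only at alpha. Option (b) avoids both losses and pays for it when the effect appears after session 6 alone: 73-89% against 81-93% for the single contrast at 50 per arm, and 40-57% against 51-67% at 25 per arm.

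**Side notes.** Name the single PVT summary score: section 5 (Measures) says "For the PVT, this file includes dependent variables for each trial, such as reaction time in milliseconds", and no summary is chosen. If a three-level F is kept as supportive, apply the Greenhouse-Geisser correction.

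### Does SAP item 1 lose its 5% error rate because it does not spell out the PVT variable, the Time levels or a CU/MCI success rule?

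*SAP*

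**What the plan says.** SAP item 1 sets the primary analysis: "Primary outcome measure (PVT) will be analyzed using mixed ANOVA with 1 between-subjects factor (Treatment Group) and 1 within subjects factor (Time"). The test of interest is the group-by-time interaction at 0.05. On the cohorts it says "Cognitively unimpaired (CU) and MCI groups will be analyzed separately". Item 1a is more specific for a secondary outcome: "Secondary outcome measures (2Back performance, % Correct and Reaction Time").

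Protocol section 5 (Measures) describes the PVT output file as holding "dependent variables for each trial, such as reaction time in milliseconds, as well as a code number indicating whether the trial was a success", "a lapse (no response in 30 seconds), or a false alarm (responded with a button press prior to the onset of the cue"). It does not nominate one of these as the endpoint.

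Protocol section 3 (treatment visits) gives three PVT occasions: "The first test will be a pre-treatment baseline evaluation"; "Then, after the first treatment with LLLT or placebo, participants will repeat the PVT and DMS tasks"; and "Participants will again repeat the PVT and DMS tasks after the sixth (final) treatment is completed".

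Protocol section 2 (Purpose) states a directional hypothesis of better performance after LLLT. It mentions both accuracy and reaction time.

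**The concern.** The primary outcome is given as a task, not a variable, while a secondary outcome has its variables named. Three matters are open on the page:

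- **Variable:** reaction time, lapses or false alarms.
- **Time levels:** all three occasions, before versus after the first treatment, or before versus after the sixth.
- **Cohort rule:** whether success needs CU, MCI, either or both.

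A 5% test exists only once the variable and the Time levels are fixed. If both were picked after the results were compared by arm, the nominal 5% would not hold in either cohort. If one overall claim for LLLT could then rest on whichever cohort was significant, the error would rise again. A primary result reached that way could not be taken at face value.

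**Working it through.** **Inputs.** Alpha 0.05 per test, the interaction test and two cohorts (SAP item 1); three PVT occasions (Protocol section 3); candidate variables reaction time, lapses and false alarms (Protocol section 5). The documents give no CU/MCI split, so cohort size is assumed (20 or 50 per arm per cohort); it barely affects the results.

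**1. The plan's own figure.** With two arms and three occasions the interaction has (2 − 1) × (3 − 1) = 2 degrees of freedom. One such test, fixed in advance, was simulated under no effect (normal data, equal correlation between occasions, 10,000 trials per setting). It was significant in 4.8% to 5.2% of trials, so the stated 5% per cohort is reproduced.

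**2. Free choice after seeing results, one cohort.** Three tests at 0.05 per variable: before vs first, before vs sixth, and the three-level interaction. The two change contrasts are taken to correlate 0.5. The entry is the chance that at least one test is significant, in either direction.

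| Variables available | Uncorrelated | r = 0.5 | r = 0.7 | r = 0.9 |
|---|---|---|---|---|
| 1 | 9.9% | – | – | – |
| 2 | 18.8% | 17.5% | 16.1% | 13.8% |
| 3 | 26.8% | 23.7% | 20.8% | 16.1% |

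**3. How firm these figures are.**

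- *Direction.* The hypothesis is that LLLT improves performance. Counting only results that favour LLLT gives about 4.5% to 5% with one variable and 13% to 15% with three uncorrelated variables. The comparable figure for one fixed two-sided contrast is 0.05 / 2 = 2.5%. The inflation is real under free choice, but a false claim of benefit is about half as likely as the table suggests.
- *Menu.* Adding first vs sixth as a fourth Time choice gives about 12% with one variable and 32% with three uncorrelated ones. The table is therefore not a ceiling; it depends on the choices assumed.
- *Variables.* The 27% end needs three uncorrelated, roughly normal measures. Success, lapse and false alarm are categories of one trial code, and a lapse requires 30 seconds without a response. Such events may well be rare (an assumption), and a sparse count would add less.
- *Time fixed, variable free.* With Time fixed at three levels, choosing among three variables gives about 10% to 14.5%.

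**4. Cohorts.** One fixed test in each of two independent cohorts gives:

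- separate claims: 5% each;
- an overall claim if either is significant: 1 − 0.95² = 9.75%;
- an overall claim only if both are significant: 0.05² = 0.25%.

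The 9.75% applies only to an overall claim that may rest on either cohort. The SAP makes no such claim.

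**5. What the documents point to.**

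- *Time:* a within-subject factor with exactly three scheduled occasions is ordinarily analysed over all three.
- *Variable:* reaction time is the measure listed first in section 5 and is named in the section 2 hypothesis.
- *Cohorts:* separate analysis most naturally means two questions, each with its own 5%.

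This reading leads back to the single test in step 1.

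**The case for a change.** The best case for a change is that all three omissions can be checked and the remedy is only wording. Section 2 names accuracy as well as reaction time, so it does not settle the variable, and no mean, median or transformation is given. The three Time options answer different questions: any difference in pattern, an acute effect, or an effect after the full course. Leaving Time open with one variable already doubles the nominal 5%. Item 1a shows that the authors could name variables when they wished.

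The omissions stand, and so does the arithmetic under its assumptions. The reaction-time reading is the least secure of the three. A sentence naming the variable and the occasions would make the primary test easier to reproduce.

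What does not stand is the step from silence to an inflated error rate. The figures need a choice made after the results are seen, and the documents show none. The proposed remedy would accept any variable and any Time levels fixed in advance, so it identifies no wrong rule and offers no better method. The cohort part is weakest: stating that CU and MCI are separate claims would repeat what separate analysis already implies and would alter no test.

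**Conclusion.** No change to the plan follows. This is a gap in detail that an analyst fills sensibly: one reaction-time measure, Time over the three scheduled occasions, CU and MCI as two questions. On that reading each cohort has one interaction test at 5%, and any other single choice fixed in advance would also keep 5%.

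The larger figures, about 10% with one variable and 16% to 27% with three, are conditional. They assume choice after the results are seen, a particular menu of three Time options, and significance counted in either direction. They are neither upper bounds nor evidence of an error in the plan. The conclusion rests on the ordinary reading being the one applied and on no overall LLLT claim being drawn from a single cohort. If a report showed the variable or occasions had been selected after comparison by arm, the objection would be to that report.
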